## 4. STATISTICAL ANALYSES

### 4.1. General Considerations

#### 4.1.1. General Methodology

Participants who prematurely withdrew from study will not be replaced.

In the case of wrong stratification assigned at the time of randomization, the analyses will be performed based on the actual stratum per data collected in the CRF.

Confidence intervals will use 95% confidence levels unless otherwise specified.

Unless otherwise specified, continuous data will be summarized using descriptive statistics: n, mean, standard deviation (std), median, minimum and maximum.

Categorical data will be summarized as the number and percentage of participants in each category.

It is anticipated that patient accrual will be spread thinly across centers and summaries of data by center would unlikely be informative and will not, therefore, be provided.

For any efficacy analyses of binary outcomes for which a risk difference will be estimated, if 100% (or 0%) success rates are observed in both treatment arms then a constant of 1E-10 will be added to each zero cell in the resultant contingency table to overcome software limitations and enable determination of the risk difference and two-sided 95% CI.

Out of stability (OOS) data may be delivered for microbiological urine samples. This data will not be included in any analysis, participants with OOS data will have their microbiological response missing and will be counted under the Unable to determine category.

Susceptibility interpretations will be based on CLSI M100 with the exception of nitroxoline and cefadroxil which are based on EUCAST guidelines and faropenem which is based on [Fuchs, 1995].

#### **4.1.2. Baseline Definition**

For all endpoints the baseline value will be the latest pre-dose assessment with a non-missing value (or randomization date in participants who are randomized but did not receive study treatment), including those from unscheduled visits. If time is not collected, Day 1 Pre-dose assessments are assumed to be taken prior to first dose and used as baseline.

For clinical signs and symptoms assessments and microbiological assessments, all Day 1 symptom assessments and urine samples (collected for identification of uropathogens) are used as baseline regardless of if they were taken pre or post dose. Urine samples collected on Day -1 or Day 1 can be considered as baseline.

Unless otherwise stated, if baseline data is missing no derivation will be performed and baseline will be set to missing. If baseline data is missing, then change from baseline calculations will not be performed and will be set to missing.

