8.1.2. Bacteriology Samples

At the Baseline Visit, a pretreatment, clean-catch midstream urine sample must be obtained from all randomized participants for Gram stain, quantitative bacteriological culture, and in vitro antimicrobial susceptibility testing at a designated central laboratory(ies). For inclusion in the micro-ITT Population, a baseline qualifying bacterial uropathogen is required as defined in Section 10.8; for inclusion in the micro-ITT NTF-S Population, the baseline qualifying uropathogen must also be susceptible to nitrofurantoin. At the On-therapy, TOC, and Follow-up Visits, a clean-catch midstream urine sample will be obtained and sent to a designated central laboratory(ies) for Gram stain, quantitative bacteriological culture, and in vitro antimicrobial susceptibility testing. Identification and susceptibility testing of isolates recovered from urine specimens at all visits will also be conducted at a designated central laboratory(ies). Additional tests, as needed, to further characterize recovered isolates will also be performed by a designated central laboratory(ies). Instructions for sample collection, processing, and shipment are provided in the SRM and the laboratory manual. The study site should follow the Microbiology Procedures section of the laboratory manual to minimize potential contamination of the specimens.

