## 3. ANALYSIS SETS

Analysis Set	Definition / Criteria	Analyses Evaluated
Screened	
 
All participants who were screened for eligibility
 
	
 
Study Population
 

Intent-to-Treat (all participants) (ITT-ALL)	
 
All participants who were randomly assigned to study treatment in the study.
 
Participants will be analyzed according to their randomized study treatment.
 
	
 
Listing
 

Intent-to-Treat (ITT)	
 
All participants in ITT-ALL population, except for participants from the site (Site ID: PPD [ ] ) due to GCP violation
 
Participants will be analyzed according to their randomized study treatment.
 
	
 
Study Population
 
Efficacy
 

Microbiological ITT (all participants) (micro-ITT-ALL)	
 
All participants randomly assigned to study treatment who receive at least 1 dose of study treatment and have a qualifying baseline uropathogen (defined in Section 6.2.10), from a quantitative bacteriological culture of a pretreatment clean-catch midstream urine specimen.
 
Participants will be analyzed according to their randomized study treatment.
 
Note that qualifying uropathogens include only the uropathogen species/groups [Gram-negative bacilli (e.g. E. coli, K. pneumoniae, P. mirabilis), S. saprophyticus, and Enterococcus spp.], defined in Section 6.2.10.
 
	
 
Listing
 

Microbiological ITT (micro-ITT)	
 
All participants in micro-ITT-ALL, except for participants from the site (Site ID: PPD [ ] ) due to GCP violation.
 
Participants will be analyzed according to their randomized study treatment.
 
	
 
Study Population
 
Efficacy
 

Micro-ITT NTF-S (all participants) (micro-ITT-ALL NTF-S)	
 
All participants in the micro-ITT-ALL Population whose baseline qualifying bacterial
 
	
 
Listing
 

Analysis Set	Definition / Criteria	Analyses Evaluated

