#### 4.2.2. Main analytical approach

The primary analysis of the primary estimand will be performed using the micro-ITT NTF-S (Entire) population.

The primary endpoint is therapeutic response (combined per-participant microbiological and clinical response) at the TOC Visit. Therapeutic success refers to participants who have been deemed both a microbiological success and a clinical success (i.e., responders).

The primary treatment effect will be estimated regardless of treatment discontinuation, as per the treatment policy strategy. The ICE of use of other systemic antimicrobial therapy is captured through the definitions of microbiological and clinical response and will be counted as failures (composite strategy). If a participant experiences both ICEs of study treatment discontinuation and use of systemic antimicrobials, then a composite strategy (assigning therapeutic response as a failure) will be used from the point that the relevant systemic antimicrobial was taken.

The number and proportion of participants achieving a therapeutic success will be presented along with its 95% Exact Clopper Pearson CI at the TOC visit and compared with the threshold for consistency with the global studies (Studies 204989 and 212390). The threshold will be derived with covariate adjustment, the covariates are the combinations of age-groups and uUTI recurrence of the participants (refer to Section 4.1.3,  $k=1, 2, 3, 4$ ). For this analysis, participants who do not return for the TOC Visit or have missing data due to any reason at the TOC Visit will be treated as failures.

1. Derive the prior for therapeutic success rate in each stratum in EAGLE2/3 studies based on the definition of stratification factor (combination of age-groups and uUTI recurrence per CRF in this study

$$p_k \sim Beta(r_{k,global}, n_{k,global} - r_{k,global})$$

, where  $n_{k,global}$  and  $r_{k,global}$  are the pooled number of participants and therapeutic responders who are assigned to the gepotidacin group of  $k^{th}$  stratum ( $k=1, 2, 3, 4$ ) in the micro-ITT NTF-S (Global) population , respectively.

2. Derive the predictive distribution for the number of participants achieving therapeutic success in each stratum  $k$ , ( $k=1, 2, 3, 4$ )

$$r_{k,Japan} \sim Beta binomial(n_{k,Japan}, \alpha = r_{k,global}, \beta = n_{k,global} - r_{k,global})$$

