**Table 10      Participant-Level Microbiological Outcome and Response Definitions per Study Visit**

Defining Criteria at the On-Therapy Visit	Outcome	Response
All qualifying baseline uropathogens have a microbiological outcome of eradication at On-therapy	Microbiological eradication	NA
At least one qualifying baseline uropathogen has an outcome of persistence at On-therapy	Microbiological persistence	NA
All qualifying baseline uropathogen outcomes are unable to determine at On-therapy	Unable to determine	NA
Defining Criteria at the TOC Visit	Outcome	Response
All qualifying baseline uropathogens have a microbiological outcome of eradication at TOC	Microbiological eradication	Microbiological success
At least one qualifying baseline uropathogen has an outcome of persistence at TOC	Microbiological persistence	Microbiological failure
At least one qualifying baseline uropathogen has an outcome of recurrence and none have an outcome of persistence at TOC	Microbiological recurrence	Microbiological failure
All qualifying baseline uropathogen outcomes are unable to determine at TOC	Unable to determine	Microbiological failure
Defining Criteria at the Follow-up Visit	Outcome	Response
All qualifying baseline uropathogens have a microbiological outcome of sustained eradication at Follow-up	Sustained microbiological eradication	Microbiological success
At least one qualifying baseline uropathogen has an outcome of recurrence and none have an outcome of persistence at Follow-up	Microbiological recurrence	Microbiological failure
At least one qualifying baseline uropathogen has an outcome of persistence at Follow-up	Microbiological persistence	Microbiological failure
At least one qualifying baseline uropathogen has an outcome of delayed eradication and none have an outcome of persistence or recurrence at Follow-up	Delayed microbiological eradication	Microbiological failure
All qualifying baseline uropathogen outcomes are unable to determine at Follow-up	Unable to determine	Microbiological failure

NA=Not applicable; TOC=Test-of-Cure.

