**Table 12      Microbiological Outcome by New Qualifying Uropathogen at the Test-of-Cure Visit**

Defining Criteria	Outcome
A new qualifying bacterial uropathogen, not identified at Baseline, is documented by quantitative urine culture at the Test-of-Cure Visit in a participant who did not achieve a clinical outcome of clinical resolution at the Test-of-Cure Visit	New infection
A new qualifying bacterial uropathogen, not identified at Baseline, is documented by quantitative urine culture at the Test-of-Cure Visit in a participant who did achieve a clinical outcome of clinical resolution at the Test-of-Cure Visit	Colonization

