#### **6.2.1.2. Clinical Outcome and Response**

Clinical signs and symptoms of acute cystitis will be recorded based on participant interview per the SoA (Protocol Section 1.3) using the scoring system and instructions ([Table 14](#)). The total cumulative symptom score is derived by summing the score for each individual sign and symptom. If any individual sign and symptom scores are missing, then total symptom score will also be missing.

At TOC, success is defined as normal presentation of signs and symptoms with a total cumulative symptom score of zero. Clinical outcome and response will be derived at On-therapy ([Table 15](#)), TOC ([Table 16](#)) and Follow-up ([Table 17](#)) Visits. Note that “resolution”, “improvement” and “worsening or no change” in total symptom score as used in the tables below are defined as:

- “Resolution”: Total cumulative symptom score is zero.
- “Improvement”: Change from baseline in total cumulative symptom score is less than zero.
- “Worsening or no change”: Change from baseline in total cumulative symptom score is greater than or equal to zero.

Note that only start date of antibiotics use will be considered when deriving the outcome and response.

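### SAP 4.1.2 accepts post-dose Day 1 urine cultures as baseline, while the micro-ITT definition requires a pretreatment specimen, and nothing says which rule governs the primary population

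*SAP*

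**What the plan says.** SAP 4.1.2 opens with a general rule: "For all endpoints the baseline value will be the latest pre-dose assessment with a non-missing value". It adds that Day 1 pre-dose assessments without a recorded time are taken to precede the first dose. It then makes an exception for symptom assessments and microbiology. Of the latter it says that, on Day 1, "urine samples (collected for identification of uropathogens) are used as baseline regardless of if they were taken pre or post dose".

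The population definitions say otherwise. SAP section 3 requires the qualifying uropathogen for micro-ITT-ALL to come "from a quantitative bacteriological culture of a pretreatment clean-catch midstream urine specimen". Micro-ITT and micro-ITT NTF-S inherit that condition. Protocol 9.2 and 10.8 carry the same requirement, and Protocol 8.1.2 says that at Baseline "a pretreatment, clean-catch midstream urine sample must be obtained from all randomized participants".

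The link to the primary result is direct: "The primary analysis of the primary estimand will be performed using the micro-ITT NTF-S (Entire) population". Participant-level microbiological success in SAP Table 10 requires that "All qualifying baseline uropathogens have a microbiological outcome of eradication at TOC".

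**The concern.** A culture taken after the first dose is a post-treatment measurement. If it may serve as baseline, two things in the primary analysis can depend on drug exposure.

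- **Who is analysed.** The culture decides whether a qualifying uropathogen is present and whether all such uropathogens are susceptible to nitrofurantoin. A participant whose organism has fallen below the qualifying count by the time of sampling would leave the primary population.
- **What counts as failure.** Eradication is required only of organisms found at baseline. An organism suppressed in a post-dose culture is not a baseline pathogen. If it regrows to a qualifying count, it falls under SAP Table 12 ("A new qualifying bacterial uropathogen, not identified at Baseline, is documented by quantitative urine culture at the Test-of-Cure Visit") and is labelled new infection or colonization, not microbiological failure.

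The primary comparison sets the gepotidacin arm alone against a threshold derived from the global studies, so randomization does not balance out such selection.

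**Working it through.** **1. The passages side by side**

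| Question | SAP 4.1.2 exception | SAP section 3; Protocol 9.2, 10.8, 8.1.2 |
|---|---|---|
| May a documented post-dose Day 1 culture be the baseline culture? | Yes | No, for micro-ITT and the sets built on it |
| Which prevails? | Not stated | Not stated |
| Which sample is used if pre-dose and post-dose cultures both exist? | Not stated; SAP 6.2.8 on multiple measurements reads as not applicable | The pretreatment one |

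SAP 4.9 does not list the exception as a change to the protocol. None of the five sensitivity analyses in SAP 4.2.3 restricts to pre-dose cultures. The exception is not needed for missing times, because 4.1.2 already covers those. What it adds is acceptance of samples known to be post-dose.

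**2. Does the symptom-score half of the exception matter?** SAP 6.2.1.2 defines resolution as "Total cumulative symptom score is zero". In Table 16 improvement and worsening are both clinical failure, and a missing baseline score still gives success if the TOC score is 0 and no antibiotics were used. A post-dose baseline score therefore only moves failures between two labels and changes baseline summaries. It does not alter the binary response.

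**3. The plan's own threshold.** Inputs from SAP section 2: 884 global gepotidacin participants, 76% response (0.76 × 884 ≈ 672 responders), n = 81 in this study. The predictive distribution is beta-binomial (81; 672, 212).

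- P(X ≤ 55) = 0.069 and P(X ≤ 56) = 0.105, so the 10th percentile is 56.
- 56/81 = 69.1%, which reproduces the stated threshold. At least 57 successes are needed.

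**4. Effect of removing participants.** The number of post-dose cultures is not in the documents. As an assumption, let m gepotidacin participants leave the set when a pre-dose culture is enforced. The threshold is recomputed at n = 81 − m.

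| m | n | Threshold count | Threshold | Results out of 81 whose verdict could change |
|---|---|---|---|---|
| 0 | 81 | 56 | 69.1% | none |
| 1 | 80 | 56 | 70.0% | 57 |
| 2 | 79 | 55 | 69.6% | 56 to 57 |
| 5 | 76 | 53 | 69.7% | 54 to 58 |
| 10 | 71 | 49 | 69.0% | 50 to 59 |

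For m from 0 to 10 the threshold stays between 68.8% and 70.0%. The last column takes the extremes, in which all those removed are successes or all are failures.

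- m = 1: 57/81 = 70.4% passes. Without one success it is 56/80 = 70.0%, which does not exceed 70.0% and fails.
- m = 1 from 56/81 (fail): 56/80 and 55/80 both fail, so one removal does not change the verdict.
- m = 2 from 56/81 (fail): without two failures it is 56/79 = 70.9% against 69.6%, a pass.

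In the plan's example the chance of exactly 57 successes is 5.0%.

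**5. Effect of a changed response.** If a regrown organism is labelled as new, one failure can become a success with n unchanged. That takes 56/81 (fail) to 57/81 (pass).

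**The case against.** The strongest reply is that the two passages can be read together. SAP 4.1.2 labels a value as baseline, and section 3 separately demands a pretreatment specimen for entry. On that reading a post-dose culture never qualifies anyone, and there is no selection. The reading is possible and may be what was meant, but no text states it. Two programmers could build different primary sets from the same SAP.

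A second reply is that the schedule of activities places the baseline culture before dosing, and Protocol section 8 describes pretreatment baseline specimens and randomizes only after pretreatment assessments. Post-dose cultures should therefore be deviations. This stands. It limits the likely size, and the existence of the exception does not show that such samples were expected.

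A third concerns biology. A reader might take the mean urine concentration in Protocol 4.3 (53.7 µg/mL against an MIC90 of 4 µg/mL, about 13-fold) as a measure of the bias. It is not one. That concentration is an 8- to 12-hour trough, whereas participants stay on site about 2 hours (1.5 to 4 hours) after the first dose. The MIC90 is for drug-resistant subsets of *E. coli*, and the protocol names AUC/MIC as the predictive index. An early drug effect on a culture is plausible but not quantified.

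Finally, the direction is open. Losing fast responders would lower the observed rate, while dropping a suppressed co-pathogen would raise it. The documents also do not give the global studies' baseline rule, so a mismatch with the data behind the threshold cannot be shown.

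**Conclusion.** The conflict is real and unresolved in the text. Applied as written, SAP 4.1.2 lets a post-treatment culture determine entry to the primary population and the set of organisms that must be eradicated. That should be corrected before the analysis.

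The practical effect is conditional. It arises only if 4.1.2 is taken to override section 3, and only for participants whose Day 1 culture used as baseline was post-dose. Their number is unknown and probably small. The verdict can change only near the threshold: at 57 of 81 for one participant removed, and 54 to 58 of 81 for five. These figures rest on the plan's example (76% of 884, n = 81, unstratified threshold). The stratified threshold of the primary analysis will differ with the actual data.

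A reader might infer three stronger claims that the documents do not support: that post-dose symptom scores distort the primary endpoint, that the primary population is already selected on treatment effect, or that one participant more or fewer would overturn a result of 56/81. The first fails on the definition of clinical response. The second depends on an unstated order of precedence. The third fails on the arithmetic: the threshold counts at n = 80, 81 and 82 are 56, 56 and 57, so 55/80, 56/80, 56/82 and 57/82 all fail.

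**What to change.** Amend SAP 4.1.2 so that, for micro-ITT, micro-ITT NTF-S and by-uropathogen response, the baseline culture is the last one collected before the first dose. Day 1 samples without a recorded time are assumed pre-dose; samples documented as post-dose do not qualify. Then:

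- report the number of post-dose Day 1 cultures by arm;
- show the current rule as a sensitivity analysis of the primary comparison;
- state whether the global studies used the same baseline rule, so that the reader can judge whether the threshold is comparable.

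If the sponsor prefers to keep the exception, it should be listed in SAP 4.9, section 3 should be reworded to match, and a sensitivity analysis restricted to confirmed pre-dose cultures should be added.

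The cost is one SAP sentence and a program flag. Protocol 6.4 and 8.4 already require the times of site dosing and of the bacteriology urination to be recorded. The downside is that a few participants may leave the primary population.

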#### **4.1.3. Strata**

Participants will be randomized to a study treatment using stratification by age category ( $\leq 50$  years, or  $>50$  years) and acute cystitis recurrence (nonrecurrent infection or recurrent infection). In the case of a difference between the stratification assigned at the time of randomization and the data collected in the eCRF, the data collected in the eCRF will be considered actual and used unless specified.

Stratification Value (k)	Stratification Description
1	$\leq 50$ years, Nonrecurrent infection
2	$\leq 50$ years, Recurrent infection
3	$>50$ years, Nonrecurrent infection
4	$>50$ years, Recurrent infection

### **4.2. Primary Endpoint(s) Analyses**

#### **4.2.1. Definition of Estimands**

Refer to Section 1.1.

#### 4.2.2. Main analytical approach

The primary analysis of the primary estimand will be performed using the micro-ITT NTF-S (Entire) population.

The primary endpoint is therapeutic response (combined per-participant microbiological and clinical response) at the TOC Visit. Therapeutic success refers to participants who have been deemed both a microbiological success and a clinical success (i.e., responders).

The primary treatment effect will be estimated regardless of treatment discontinuation, as per the treatment policy strategy. The ICE of use of other systemic antimicrobial therapy is captured through the definitions of microbiological and clinical response and will be counted as failures (composite strategy). If a participant experiences both ICEs of study treatment discontinuation and use of systemic antimicrobials, then a composite strategy (assigning therapeutic response as a failure) will be used from the point that the relevant systemic antimicrobial was taken.

The number and proportion of participants achieving a therapeutic success will be presented along with its 95% Exact Clopper Pearson CI at the TOC visit and compared with the threshold for consistency with the global studies (Studies 204989 and 212390). The threshold will be derived with covariate adjustment, the covariates are the combinations of age-groups and uUTI recurrence of the participants (refer to Section 4.1.3,  $k=1, 2, 3, 4$ ). For this analysis, participants who do not return for the TOC Visit or have missing data due to any reason at the TOC Visit will be treated as failures.

1. Derive the prior for therapeutic success rate in each stratum in EAGLE2/3 studies based on the definition of stratification factor (combination of age-groups and uUTI recurrence per CRF in this study

$$p_k \sim Beta(r_{k,global}, n_{k,global} - r_{k,global})$$

, where  $n_{k,global}$  and  $r_{k,global}$  are the pooled number of participants and therapeutic responders who are assigned to the gepotidacin group of  $k^{th}$  stratum ( $k=1, 2, 3, 4$ ) in the micro-ITT NTF-S (Global) population , respectively.

2. Derive the predictive distribution for the number of participants achieving therapeutic success in each stratum  $k$ , ( $k=1, 2, 3, 4$ )

$$r_{k,Japan} \sim Beta binomial(n_{k,Japan}, \alpha = r_{k,global}, \beta = n_{k,global} - r_{k,global})$$

, where  $n_{k,Japan}$  and  $r_{k,Japan}$  are the number of participants and therapeutic responders who are assigned to the gepotidacin group of  $k^{th}$  stratum in the micro-ITT NTF-S population, respectively.

3. Derive lower 10 percentile as a threshold using simulation

a. Set  $j = 1$

b. Sample  $r_{k,Japan}^{(j)}$  from  $Beta binomial(n_{k,Japan}, \alpha = r_{k,global}, \beta = n_{k,global} - r_{k,global})$  for each stratum ( $k = 1, \dots, 4$ )

- c. Calculate  $r_{Japan}^{(j)} = r_{1,Japan}^{(j)} + r_{2,Japan}^{(j)} + \dots + r_{4,Japan}^{(j)}$  and set  $j \leftarrow j + 1$
- d. Repeat the step b and c until  $j = 1,000,000$ .
- e. Obtain the lower 10th percentile value  $(r_{Japan}^{(10\%)})$  of  $r_{Japan}^{(j)}$
- f. Calculate the threshold as  $r_{Japan}^{(10\%)} / n_{Japan}$  where  $n_{Japan}$  is the number of participants in the gepotidacin group.

